5.2 RESCUE TREATMENT

At 2 hours post-dose, if the subject has headache pain such that additional treatment is desired, subjects treating with their Usual Triptan will be permitted to take a second dose of their Usual Triptan, or their usual care rescue medication (however, no NSAIDS or other triptans would be permitted as a rescue treatment). For subjects treating with Treximet™, who have headache pain such that additional treatment is desired at 2 hours post dose, subjects may treat with a second Treximet™tablet or their usual care rescue medication (however, no NDAIDS or other triptans would be permitted as a rescue treatment). Subjects in both treatment arms may, at 24 hours post initial dose, take a second dose tablet, (if a second dose [usual triptan or Treximet™tablet] has not already been taken),when headache pain continues to require treatment. No more than 2 Treximet™ tablets are permitted to treat one migraine.

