3 INVESTIGATIONAL PLAN

3.1 SUMMARY OF STUDY DESIGN

This is a single site, randomized, open-label, two arm, crossover, study of subject productivity improvement and satisfaction with migraine treatment using Treximet™ vs usual triptan.

This study will recruit 60 patients who are employed in a paying job, who have episodic migraine (<15 days/month), who are using acute care triptan monotherapy for their migraine (excluding combinations of any sort, such as acetaminophen [APAP] and non-steroidals [NSAIDs]) and who have no contraindications to triptan or NSAID use.

In one arm of the study, patients will treat 3 work day migraines with their usual triptan and in the other arm of the study the same patients will treat 3 work day migraines with Treximet. The medication that they use in the first arm of the study is determined by randomization. They will maintain headache diaries for the duration of the study and fill out the WPAI after each work day migraine. After treating 3 work day migraines, they will also fill out CORS Part 1 and Migraine-ACT.

Between the completion of the 3rd migraine attack treatment, and the start of the second treatment arm, there will be a minimum of a 48 hour washout period and an office visit.

In the second arm, after cross over to the other treatment, the sixty patients will maintain headache diaries, treat 3 attacks during any day in which they are scheduled to work, and fill out the WPAI after each attack. Additionally, after 3 attacks are treated, they will fill out CORS Part 1, CORS Part 2 and Migraine-ACT. This second arm differs from arm one in that the subjects will treat their migraines with the other medication from that assigned in the first arm.

Subject participation will last approximately 3 months, depending on the days needed to treat migraines during the workday according to protocol.

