4. SUBJECT SELECTION

4.1 NUMBER OF SUBJECTS

This study will enroll 60 subjects for participation. There are no other sites for this study.

The sample size was chosen to be a sufficient number to assess the effect of Treximet on the WPAI using a crossover design in which patients will serve as their own controls.

Based on previous GSK studies on Treximet utilizing the WPAI, the effect size between Treximet and usual triptan care is expected to be small. In those studies, comparisons of Treximet to placebo yielded differences of 0.4 to 1.4. For this study, a one-point WPAI difference between Treximet and triptan is assumed to be clinically meaningful. Furthermore, the GSK Treximet studies were parallel designs with standard deviations ranging from 2.5 to 3.5. To account for the correlation from patients acting as their own controls in this crossover design, a standard deviation of the difference equal to 2.5 is assumed. Under these assumptions, a total sample of 60, with 30 in each sequence, would power the study at 86%.

4.2 INCLUSION CRITERIA:

A subject will be eligible to participate in this study if all of the following criteria apply:

1. subject is 18 years or older at screening
2. subject has a history of migraine greater than 1 year
3. subject has been diagnosed with migraine before age 50
4. subject is an employed person (is paid wages for his/her work)

5. subject has diagnosis of episodic migraine, by IHS criteria
6. subject uses triptan monotherapy as the primary migraine abortive treatment
7. subject is not pregnant or nursing

4.3 EXCLUSION CRITERIA:

A subject will not be eligible to participate in this study if any of the following criteria apply:

1. subject is less than 18 years of age at screening
2. subject does not have history of migraine greater than 1 year
3. subject was diagnosed with migraine after age 50
4. subject is not currently employed
5. subject does not have diagnosis of episodic migraine
6. subject does not use triptan monotherapy as primary migraine abortive treatment
7. subject is pregnant or nursing
8. subjects with a history of stroke, myocardial infarction (including vasospastic coronary artery disease [CAD] or cardiovascular thrombotic events)
9. subjects with gastrointestinal disease history to include ulcers, bleeding or perforations of the stomach or intestines
10. subjects with a history of significant renal or hepatic disease.

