2 DOSAGE AND ADMINISTRATION

2.1 Dosage in Adults

The recommended dosage for adults is 1 tablet of TREXIMET 85/500 mg. TREXIMET 85/500 mg contains a dose of sumatriptan higher than the lowest effective dose. The choice of the dose of sumatriptan, and of the use of a fixed combination such as in TREXIMET 85/500 mg should be made on an individual basis, weighing the possible benefit of a higher dose of sumatriptan with the potential for a greater risk of adverse reactions.

The maximum recommended dosage in a 24-hour period is 2 tablets, taken at least 2 hours apart.

The safety of treating an average of more than 5 migraine headaches in adults in a 30-day period has not been established.

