7.3 Other 5-HT₁ Agonists

Because their vasospastic effects may be additive, coadministration of TREXIMET and other 5-HT₁ agonists (e.g., triptans) within 24 hours of each other is contraindicated.

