Inform patients that TREXIMET, like other NSAID-containing products, may increase the risk of serious skin side effects such as exfoliative dermatitis, Stevens-Johnson syndrome, and toxic epidermal necrolysis, which may result in hospitalizations and even death. Although serious skin reactions may occur without warning, patients should be alert for the signs and symptoms of skin rash and blisters, fever, or other signs of hypersensitivity such as itching and should ask for medical advice when observing any indicative signs or symptoms. Advise patients to stop the drug immediately if they develop any type of rash and contact their healthcare providers as soon as possible [*see Warnings and Precautions (5.13)*].

Pregnancy

Inform patients that TREXIMET should not be used during the third trimester of pregnancy because NSAID-containing products have been shown to cause premature closure of the ductus arteriosus. Inform patients that TREXIMET should be used during the first and second trimester of pregnancy only if the potential benefit justifies the potential risk to the fetus [*see Contraindications (4), Warnings and Precautions (5.14), Use in Specific Populations (8.1)*].

Nursing Mothers

Advise patients to notify their healthcare provider if they are breastfeeding or plan to breastfeed [*see Use in Specific Populations (8.3)*].

Hepatotoxicity

Inform patients of the warning signs and symptoms of hepatotoxicity (e.g., nausea, fatigue, lethargy, pruritus, jaundice, right upper quadrant tenderness, and “flu-like” symptoms). Instruct patients to stop therapy and seek immediate medical therapy if these signs and symptoms occur [*see Warnings and Precautions (5.15)*].

Concomitant Use with Other Triptans or Ergot Medications

Inform patients that use of TREXIMET within 24 hours of another triptan or an ergot-type medication (including dihydroergotamine or methysergide) is contraindicated [*see Contraindications (4), Drug Interactions (7.1, 7.3)*].

Serotonin Syndrome

Caution patients about the risk of serotonin syndrome with the use of TREXIMET or other triptans, particularly during concomitant use with SSRIs, SNRIs, TCAs, and MAO inhibitors [*see Warnings and Precautions (5.10), Drug Interactions (7.3, 7.6)*].

Medication Overuse Headache

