- Certain people should take their first dose of TREXIMET in their healthcare provider's office or in another medical setting. Ask your healthcare provider if you should take your first dose in a medical setting.
- Take TREXIMET exactly as your healthcare provider tells you to take it.
- Take TREXIMET tablets whole with water or other liquids.
- TREXIMET can be taken with or without food.
- If you do not get any relief after your first dose, do not take a second dose without first talking with your healthcare provider.
- If your headache comes back or you only get some relief from your headache:
 - For adults: a second dose may be taken 2 hours after the first dose. Do not take more than 2 doses of TREXIMET 85/500 mg in a 24-hour period.
 - For children 12 to 17 years of age: it is not known if taking more than 1 dose of TREXIMET in 24 hours is safe and effective. Talk to your healthcare provider about what to do if your headache does not go away or comes back.
- If you take too much TREXIMET, call your healthcare provider or go to the nearest hospital emergency room right away.
- You should write down when you have headaches and when you take TREXIMET so you can talk with your healthcare provider about how TREXIMET is working for you.

What should I avoid while taking TREXIMET?

TREXIMET can cause dizziness, weakness, or drowsiness. If you have these symptoms, do not drive a car, use machinery, or do anything where you need to be alert.

What are the possible side effects of TREXIMET?

TREXIMET may cause serious side effects. See "What is the most important information I should know about TREXIMET?"

These serious side effects include:

- changes in color or sensation in your fingers and toes (Raynaud's syndrome)
- heart failure from body swelling (fluid retention)
- kidney problems including kidney failure
- low red blood cells (anemia)
- liver problems including liver failure
- asthma attacks in people who have asthma
- stomach and intestinal problems (gastrointestinal and colonic ischemic events). Symptoms of gastrointestinal and colonic ischemic events include:
 - sudden or severe stomach pain
 - weight loss
 - constipation or diarrhea
 - fever
 - stomach pain after meals
 - nausea or vomiting
 - bloody diarrhea
- problems with blood circulation to your legs and feet (peripheral vascular ischemia). Symptoms of peripheral vascular ischemia include:
 - cramping and pain in your legs or hips
 - feeling of heaviness or tightness in your leg muscles

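### Section 5 sets no 24-hour rule for Treximet and the usual triptan across separate migraines, although the label appended to the protocol does

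*Combined protocol and SAP*

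**What the plan says.** Section 5.1 has the patient take one Treximet tablet when the headache starts, or the usual triptan at its prescribed dose, for each of 3 work-day migraines per period. It sets no condition on when a triptan was last taken.

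Section 5.2 allows further treatment from 2 hours. For a migraine treated with Treximet it says that "no NDAIDS or other triptans would be permitted as a rescue treatment", and it ends with the cap "No more than 2 Treximet™ tablets are permitted to treat one migraine".

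Section 3.1 and the flow chart in Section 6 place a washout of at least 48 hours between the third treated attack of the first period and the start of the second. Patients arrive as triptan users: inclusion criterion 6 in Section 4.2 is that "subject uses triptan monotherapy as the primary migraine abortive treatment".

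The label in Appendix 11.6 sets its limits by the clock. Its Section 2.1 reads "The maximum recommended dosage in a 24-hour period is 2 tablets, taken at least 2 hours apart". Its Sections 4 and 7.3 contraindicate another triptan within 24 hours, and its Section 17 tells the prescriber: "Inform patients that use of TREXIMET within 24 hours of another triptan or an ergot-type medication (including dihydroergotamine or methysergide) is contraindicated". The Medication Guide in the same appendix says "Do not take more than 2 doses of TREXIMET 85/500 mg in a 24-hour period".

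Section 5.3.4 relies on the study diary to record treatment use for the treated attacks.

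**The concern.** The protocol's dosing section and its appended label work in different units. The protocol counts by migraine; the label counts by hours. The two agree while attacks are well separated. They part when two migraines fall within 24 hours and only one of them is a Treximet-treated study attack, or when both are.

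Patients dose themselves away from the clinic; the flow chart marks only Visits 1, 5 and 9 as office visits. The instruction they carry therefore has to be complete. What is at stake is a drug combination that the label contraindicates, taken by someone who is following Section 5 correctly, with no record from which anyone could later tell.

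**Working it through.** The plan gives no figure on this point, so there is none to reproduce. The check is to list the ways in which Treximet and another triptan, or too many Treximet tablets, could fall within 24 hours, and to see which rule covers each.

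1. *Usual triptan as rescue after Treximet, same migraine.* Barred by Section 5.2. Closed, except that the phrase about other triptans is unclear when the usual triptan is itself sumatriptan.
2. *Last study attack of period 1, then the other drug in period 2.* The washout is at least 48 hours, longer than 24. Closed.
3. *Usual triptan shortly before the first Treximet dose, Treximet-first patients.* No washout is stated before period 1. Open. Appendix 11.7 has 30 rows with Treximet first and 30 with the triptan first (30 + 30 = 60), so this applies to 30 of 60 patients.
4. *Usual triptan for a non-study migraine after the washout but before the first Treximet dose, triptan-first patients.* The washout is counted from the third study attack and does not address a later migraine. Open.
5. *Usual triptan for a weekend or other non-study migraine during the Treximet period.* Section 5 names no drug for such migraines and sets no interval. Open, for all 60 patients.
6. *Treximet for two separate migraines within 24 hours.* The per-migraine cap starts afresh with the second migraine. Open.

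Exclusion criterion 15 in Section 4.3, on use of 5-HT agonists, cannot serve as a timing rule. Read literally, it would exclude the triptan users whom inclusion criterion 6 requires.

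For route 6 the tablet count is as follows.
- Cap alone, two migraines: 2 × 2 = 4 tablets.
- Supply: Section 5.3 describes one bottle of 3, meant for initial doses. If that is all the patient holds, and one of these tablets is used as a second dose, the most is 2 + 1 = 3.
- Sumatriptan: 3 × 85 = 255 mg, against the label maximum of 2 × 85 = 170 mg.
- Naproxen sodium: 3 × 500 = 1,500 mg, against 2 × 500 = 1,000 mg.
- Ratio: 3/2 = 1.5 times the label maximum.

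The diary entry in Appendix 11.5 asks for date, day, headache yes or no, start time, stop time and pain level at dosing. It has no place for the drug, the time of the dose or the number of tablets. Concomitant medication is reviewed at Visits 1, 5 and 9, and Treximet containers are returned. Neither is described as giving dose times. So neither 24-hour limit can be checked from the records that the plan describes.

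**The case against.** The strongest reply is that the label is part of the protocol. Appendix 11.6 states both limits, instructs that patients be told of the triptan contraindication, and includes a Medication Guide that puts both limits in patient language. Nothing in Section 5 overrides them. The consent pages are not among the documents reviewed, so what patients were told cannot be judged. On this view Section 5 merely fails to repeat its own appendix. Much of this stands and is why the point is minor. It does not remove the point: Section 5 writes its own dosing rule in other units and neither cites nor adopts the label's limits.

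A second reply is that the obvious routes are already closed, and that is correct. A reader might infer that the protocol leaves patients free to mix the usual triptan with Treximet. The documents do not support that: the rescue bar covers the same migraine and the washout covers the crossover. Section 5.2 also matches the label's 2-hour spacing, and for a migraine lasting beyond 24 hours its cap is stricter than the label's.

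A third reply is that nothing shows the situation to be common. That also stands. The limit of fewer than 15 days a month in Section 3.1 is a ceiling on days and says nothing about spacing. Section 3.1 foresees 6 study attacks in about 3 months, or 6/3 = 2 a month.

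Finally, the three-tablet case is remote. It needs two work-day attacks within 24 hours and the use of initial-dose tablets as second doses. Label Section 10 reports 670 patients given single doses of 140 to 300 mg sumatriptan without significant adverse effects, a range that contains 255 mg. That passage does not address two different triptans taken within 24 hours.

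**Conclusion.** The point holds as a minor safety gap. Section 5 lacks a 24-hour separation between Treximet and the usual triptan for a new, non-study or pre-first-dose migraine, and lacks a 24-hour Treximet maximum. The appended label sets both. The diary on which Section 5.3.4 depends could not reveal a breach of either.

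The gap reaches all 60 patients in their Treximet period, and 30 of them have no stated washout before it. No frequency and no expected harm can be derived from the documents. A reader might infer a shown hazard, frequent overdosing, or patients left uninformed; none of these is supported. The three-tablet figure of 1.5 times the label maximum is conditional and secondary; the main case is usual triptan and Treximet for two neighbouring migraines.

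The conclusion assumes that the diary pages are complete as printed and that no separate patient instruction, unseen here, already carries the limits. If one does, the Section 5.2 wording should still be brought into line with it.

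**What to change.** Add to Section 5.2, and print on the diary in Appendix 11.5:

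> Do not take Treximet within 24 hours after any dose of your usual triptan (including sumatriptan) or any other triptan, and do not take any of these within 24 hours after Treximet, for any migraine. Take no more than 2 Treximet tablets in any 24 hours, at least 2 hours apart, across all migraines. A migraine for which the assigned drug is not allowed under these limits is not a study attack; treat it with the drug already in use, within its label, or with non-triptan, non-NSAID rescue.

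Add one line to each diary entry: *Each migraine medicine taken: name, time, number of tablets.* Report by treatment the number of attacks not counted for this reason.

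A broader rule, discarding in both periods every attack with any triptan or Treximet use in the previous 24 hours, looks even-handed but should not be adopted. Such use depends on how well the earlier headache was controlled. Label Section 14.1 reports sustained pain-free rates of 25% and 23% with Treximet against 16% and 14% with sumatriptan alone. Discards could therefore differ by treatment and change which attack is the last one, on which the primary outcome in Section 8.2 rests.

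The narrower rule has a smaller version of the same cost. A few close-spaced attacks may be unusable, mainly in the Treximet period, which may then run slightly longer. Those attacks could not be treated with Treximet within the label in any case, and the reported count shows whether the imbalance matters. Visits, the 2-hour second-dose rule and the sample size do not change.

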5.3 STUDY DRUG SUPPLY

For the treatment period when the subjects are taking Treximet™, they will be dispensed a study drug bottle containing 3 Treximet™ tablets for initial dosing (1 tablet dose) of 3 migraines during the work day.

5.3.1 Treatment Assignment will be made according to the randomization schedule created by Quantitative Health Sciences at Cleveland Clinic.

5.3.2 Treatment will be open label.

5.3.3 For study product accountability, subjects will have documented dispensation of study product and will return study drug containers at the office visit following the Treximet™ treatment arm completion.

5.3.4 Subjects will record treatment use in study diaries for the treated migraine attacks.

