5 STUDY DOSAGE/DOSAGE REGIMEN

5.1 INITIAL TREATMENT

Subjects will take a single dose of Treximet™ (1 tablet, which is 85mg of sumatriptan and 500mg of naproxen sodium) at headache onset, or Usual Triptan (at regular prescribed dose) to treat each of 3 migraines occurring during the work day.

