6 STUDY ASSESSMENTS

The Study Flowsheet (time and events table) provided below lists the study activities throughout the protocol.

STUDY FLOW CHART			
		Washo	

	Screen (Office Visit)	First Arm (Treximet™ or Usual Triptan) - Treat 3 Migraines			ut Windo w (at least 48h post V4 tx) (Office Visit)	Second Arm (Treximet™ or Usual Triptan) - Treat 3 Migraines			EOS (Office Visit)
Procedure	Visit 1	Visit 2	Visit 3	Visit 4	Visit 5	Visit 6	Visit 7	Visit 8	Visit 9
Informed Consent	X								
Inclusion/Exclusion	X								
Office Visit (PE, Vitals Neuro Exam)	X								X
Urine Pregnancy Test (if female and childbearing potential)	X				X				X
Conmeds	X				X				X
AE/SAE collect					X				X
Migraine History & update	X				X				
Medical History- & update	X				X				X
Educ/Disp/Revu Diary	X	X	X	X	Collect	x	x	x	Collect
Randomization	X				Switch TX Arm				
Disp/Take/Collect Study Drug	X	X	X	X	Collect	X	X	X	Collect
WPAI		X	X	X	Collect	X	X	X	Collect
CORS 1				X	Collect			X	Collect
CORS 2								X	Collect
MigraineAct	X			X	Collect			X	Collect
KP Data	X				X				X

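### Section 5.2 permits up to six Treximet tablets over three attacks, but 5.3 supplies three for first doses and names no source for second ones; separately, the diary has no line for re-dosing, rescue or adverse events

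*Combined protocol and SAP*

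**What the plan says.** Section 5.1 sets one Treximet tablet, or "Usual Triptan (at regular prescribed dose) to treat each of 3 migraines occurring during the work day".

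Section 5.2 covers what may follow. Two hours after a Treximet dose, "subjects may treat with a second Treximet™tablet or their usual care rescue medication", with NSAIDs and other triptans barred as rescue. In the usual-triptan period the corresponding choice is a second dose of that triptan or usual-care rescue, with the same bar. If no second dose has been taken by then, "Subjects in both treatment arms may, at 24 hours post initial dose, take a second dose tablet". The ceiling is stated: "No more than 2 Treximet™ tablets are permitted to treat one migraine".

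Section 5.3 supplies the drug. The subject is "dispensed a study drug bottle containing 3 Treximet™ tablets for initial dosing (1 tablet dose) of 3 migraines", and under 5.3.3 "will return study drug containers at the office visit following the Treximet™ treatment arm completion". The flow chart in Section 6 has a row "Disp/Take/Collect Study Drug" marked across both periods, but it gives no quantities. How the usual triptan is obtained is not stated.

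On records, 5.3.4 says "Subjects will record treatment use in study diaries for the treated migraine attacks", and 6.2 names the diary, together with office visits, as a source of adverse events. The form in Appendix 11.5 asks for date, day, headache yes/no, start and stop times, and pain at dose time. Section 8.2 makes the WPAI score after the last attack the primary outcome and plans a sensitivity model using all three attacks.

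**The concern.** The dosing rule and the supply rule do not match, and two things can follow. If the bottle is kept for first doses, a dose that the protocol permits is not provided. The Treximet period then offers one study dose per attack, while the usual-triptan period may offer two. That difference would come from logistics, inside the comparison the trial is meant to make. If instead a bottle tablet is used as a second dose at attack 1 or 2 and not replaced, none remains for attack 3. The lost record would be the primary one, lost in the Treximet period only, and lost because early response was poor.

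The diary gap is a separate defect, but it bears on the first. The form cannot show which attack was re-dosed or rescued, so the trial could not tell from it whether the supply problem occurred or whether the rescue rules were followed.

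**Working it through.** **Plan's own figures.** First doses: 3 attacks × 1 tablet = 3, which matches 5.3. Power in Section 4.1: difference 1, SD of the difference 2.5, n = 60, two-sided 0.05. The noncentrality is 1/(2.5/√60) = 1/0.3227 = 3.10. With 58 df the noncentral t gives 86.1%, matching the stated 86%.

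**Tablet count.** Permitted: 3 × 2 = 6. Supplied: 3. Gap: at most 3 per subject, or 3 × 60 = 180 for the trial.

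**Branch A: bottle kept for first doses.** Every attack has its first tablet, so no third attack is lost and power is unaffected. What is lost is the second Treximet dose. The documents give nothing from which to size the effect on the WPAI.

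**Branch B: second tablets taken from the bottle, no resupply.** A second tablet at attack 1 or 2 leaves none for attack 3. The documents give no re-dose rate, so assume a fraction q of attacks of 5%, 10% or 20%.

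- Independent attacks: share without a Treximet third attack = 1 − (1 − q)², and pairs left = 60 × (1 − q)².
- Correlated attacks: simulation of 1,000,000 patients, three attacks per treatment, SD 2.5, correlation 0.5 (so SD of the difference = 2.5), no true treatment effect, and a second tablet when the attack's score is in the worst q.
- Power is for complete pairs, by noncentral t with n − 2 df.

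| q | Missing, independent | Pairs | Power | Missing, correlated | Pairs | Power |
|---|---|---|---|---|---|---|
| 5% | 9.75% | 54.2 | 82.4% | 8.8% | 54.7 | 82.8% |
| 10% | 19% | 48.6 | 78.0% | 16.8% | 49.9 | 79.1% |
| 20% | 36% | 38.4 | 67.5% | 31.3% | 41.2 | 70.7% |

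Bias with no true effect (negative favours Treximet, meaning less lost time):

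| Analysis | q = 5% | 10% | 20% |
|---|---|---|---|
| Complete pairs | within 0.01 of 0 | same | same |
| Last-attack mixed model, variance components estimated | −0.12 | −0.22 | −0.38 |
| Same, correlation fixed at 0.5 | −0.11 | −0.20 | −0.35 |
| Estimated components, attack correlation 0.3 | −0.11 | −0.20 | −0.34 |
| Estimated components, attack correlation 0.7 | −0.09 | −0.17 | −0.29 |
| Half of re-doses replaced by usual-care rescue | −0.06 | −0.11 | −0.18 |
| Re-dose trigger correlated 0.5 with score | −0.07 | −0.12 | −0.20 to −0.22 |
| Re-dose trigger correlated 0.3 with score | −0.04 | −0.07 | −0.12 to −0.13 |
| Last treated attack used as the last attack | +0.11 | +0.17 | +0.24 |
| All-attack model | within 0.003 of 0 | same | same |

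The pattern has a simple cause. Whether attack 3 is missing depends on Treximet attacks 1 and 2. The last-attack model does not contain those scores. It keeps the usual-triptan records of patients who tend to score badly without their Treximet counterparts. Complete pairs cancel the patient effect, and the all-attack model contains the scores that drive the loss. Taking the last treated attack instead substitutes attack 2, which is sometimes the bad attack that triggered the second tablet, so the sign reverses. These rows belong to different analyses and do not add up.

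**Diary.** Set 5.3.4 and 6.2 against the form: there is no line for drug taken, second dose, rescue or adverse events.

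**The case against.** The strongest reply is that the bottle is described as being for first doses. A patient who follows that has a tablet for attack 3, and none of the Branch B figures applies. This stands. A reader might infer that the plan as written leaves attack 3 untreated and biases the result toward Treximet; the documents do not support that. It needs patients to use first-dose tablets as second doses, and it needs no resupply, a point on which the flow chart row is silent.

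Second, the larger bias figures let re-dosing track the WPAI score exactly. Section 5.2's trigger is headache pain at 2 or 24 hours, whereas the outcome is work and activity time lost, recorded at bedtime. The two are related but not the same, and a looser link shrinks the bias to roughly a third to three-fifths. Usual-care rescue, and the Medication Guide's advice not to re-dose after no relief without first speaking to a healthcare provider, would lower the rate further. The direction also turns on how the last attack is read, and the planned all-attack model is about unbiased. All of this stands, and it limits the size of the problem. It does not supply the missing tablet.

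Third, the diary gap is partly covered. Treatment is open label with a known drug in each period, the WPAI is dated on the treated day, containers are returned, and adverse events and concomitant medication are collected at office visits. A reader might infer that adverse events go uncollected; they do not. What cannot be recovered is second-dose and rescue use by attack. No planned analysis uses either, so no planned estimate changes on that account.

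**Conclusion.** The concern holds in a limited form. The mismatch between 5.2 and 5.3 is a matter of plain count: six permitted, three supplied, no source for the rest. On the plain reading the consequence is a rescue difference between periods of unknown size, assuming that the usual triptan is the patient's own prescription.

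Loss of the primary attack is conditional on re-dosing from the bottle without resupply. Under that condition, and at assumed rates of 5% to 20%, about 9% to 36% of patients lack a Treximet third attack and complete-pair power is about 67% to 83%. The last-attack mixed model is biased by about 0.04 to 0.38 points toward Treximet, depending mainly on the rate and on how closely re-dosing tracks the score. If the last treated attack is used and re-dosing tracks the score exactly, the bias is about 0.11 to 0.24 points against Treximet.

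The diary gap is certain on the face of the form and limited in effect. Both should be corrected, since the change is specific and cheap. Confidence in the size is medium at best, because every rate and correlation is assumed.

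**What to change.** In 5.3, dispense six tablets for the Treximet period. Label and reserve three for the first doses of the three study attacks and three for second doses only, with unused tablets returned. The reservation matters: six unmarked tablets would let patients treat more than three attacks with Treximet.

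In Appendix 11.5, add lines for second dose (time), rescue medication (name, time) and adverse events.

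The cost is at most 180 more tablets for 60 subjects, a wording and labelling change, and a slightly longer diary page. No visits or staff are added. If the extra tablets cannot be provided, 5.3 should name another source for second doses or 5.2 should drop the option; dropping it would make the rescue difference between periods explicit but would not remove it.
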